2. STUDY OBJECTIVES

2.1. **PRIMARY OBJECTIVE**

The primary objective is to assess the efficacy of namilumab 150 mg subcutaneous (sc), given on Weeks 0, 2, 6 and 10 in subjects with axial spondyloarthritis (axSpA)

2.2. **SECONDARY OBJECTIVES**

- To assess the efficacy of namilumab 150 mg sc, given on Weeks 0, 2, 6 and 10 on other clinical responses in subjects with axSpA
- To assess the safety and tolerability of namilumab 150 mg sc, given on Weeks 0, 2, 6 and 10 in subjects with axSpA

2.3. **EXPLORATORY OBJECTIVES**

- To assess the efficacy of namilumab 150 mg sc, given on Weeks 0, 2, 6 and 10 on radiologic responses in subjects with axSpA
- To assess the effect of namilumab 150 mg sc, given on Weeks 0, 2, 6 and 10 on other clinical responses, biomarkers, immunophenotyping, and pain scores in subjects with axSpA

Document:	x:\biostatistics\documentation\sap\pya18238_izana_ izn-101	_sap_v1_0_2019050.docx	
Author:		Version Number:	1.0
		Version Date:	07May2019
Template No.:	CS_TP_BS016 Revision 5	Reference: CS_WI	BS00

Template No.: CS_TP_BS016 Revision 5

Effective Date: 01Apr2018

1.0

07May2019

Reference: CS WI BS00

3. STUDY DESIGN

3.1. GENERAL DESCRIPTION

Overall Design:

This is a proof-of-concept, randomised, double-blind, placebo-controlled, multi-centre study designed to evaluate the safety/tolerability and efficacy of 4 sc injections of namilumab 150 mg given over 10 weeks as therapy in subjects with moderate-to-severely active axSpA, including those with a history of inadequate response to or intolerance of anti-TNF therapy. The study will allow enrolment of up to 50% of subjects with primary non-response to prior anti-TNF treatment. The study will consist of a maximum 4-week Screening Period, followed by a 12-week double-blind treatment evaluation period, followed by a 16-week safety follow-up period.

Number of Subjects:

Approximately 70 subjects will be screened to achieve 42 subjects randomly assigned to study treatment (36 on active treatment and 6 on placebo) and 42 evaluable subjects for an estimated total of 36 evaluable subjects on the active treatment arm and 6 evaluable subjects in the placebo treatment arm. Randomisation will be stratified by prior use of anti-TNF agents.

Treatment Groups and Duration: Test product, dose and mode of administration: Namilumab 150 mg sc administered at Day 1 of Weeks 0, 2, 6 and 10. Reference therapy, dose and mode of administration: Matching placebo solution sc administered at Day 1 of Weeks 0, 2, 6 and 10.

 Document:
 x:\biostatistics\documentation\sap\pya18238_izana_izn-101_sap_v1_0_2019050.docx

 Author:
 Version Number:

Template No.: CS_TP_BS016 Revision 5

Effective Date: 01Apr2018

Copyright © 2009, 2010, 2012, 2016, 2018 IQVIA. All rights reserved. The contents of this document are confidential and proprietary to IQVIA Holdings Inc. and its subsidiaries. Unauthorized use, disclosure or reproduction is strictly prohibited.

Version Date:

Page 12 of 36

Table A:Study Schema

3.2. SCHEDULE OF EVENTS

Schedule of events can be found in Section 1.3 of the protocol.

3.3. CHANGES TO ANALYSIS FROM PROTOCOL

Full analysis set modified

- The full analysis set (FAS) was defined in the protocol as "All subjects randomly assigned to study treatment and who take at least 1 dose of study treatment and have specific post-baseline assessments available". This has been updated in Section 5.3 of this SAP to be "The full analysis set (FAS) will contain all subjects in the all randomised set (RND) who received at least one dose of study medication".
- The reason for this change is that all subjects with missing data at week 12 for efficacy will be considered as non-responders (as per protocol definition) thus they will all be included in the FAS if randomised and treated.
- Date of agreement of change is 12April2019

Document:	x:\biostatistics\documentation\sap\pya18238_izana_izn-10	1_sap_v1_0_2019050.docx	
Author:		Version Number:	1.0
		Version Date:	07May2019
Template No.: CS_TP_BS016 Revision 5		Reference: CS_W	I_BS00

Effective Date: 01Apr2018

Per-protocol analysis set modified

- The per protocol analysis set was defined in the protocol as "All subjects in the Full Analysis Set that have week 10 efficacy data." This has been updated in Section 5.3 of this SAP to be "The per-protocol analysis set (PPAS) will contain all subjects in the COM who did not experience any protocol deviations that might affect the efficacy results."
- The reasons for this change are that there was a typographical error in the definition (week 10 instead of week 12) and that the goal of the per-protocol analysis is also to investigate the effect of the compound under investigation in patients who did not violate the protocol.
- Date of agreement of change 12April2019

Interim analysis for strategic purposes

- An interim analysis for strategic purposes is added to obtain preliminary results once all randomized subjects have completed the week 12 assessments.
- Date of agreement of change 12April2019

Primary endpoint definition amendment

- The definition has been amended to: "A subject with an improvement from baseline of at least 20% and an absolute improvement of at least 10 units on a 0-100 VAS in at least 3 of the following four domains collected on the eCRF and no worsening in the fourth domain."
- The amendment is due to an improper definition in the protocol.
- Date of agreement of change 12April2019

ASAS70 analysis removed

- ASAS70 endpoint has been removed as it is not a validated measure
- Date of agreement of change 12April2019

4. PLANNED ANALYSES

Interim analysis. Final analysis.

Document:	x:\biostatistics\documentation\sap\pya18238_izana_ izn-101	_sap_v1_0_2019050.docx	
Author:		Version Number:	1.0
		Version Date:	07May2019
Template No.:	CS TP BS016 Revision 5	Reference: CS WI	BS00

Effective Date: 01Apr2018

Page 14 of 36

4.1. DATA MONITORING COMMITTEE (DMC)

There will be no DMC for this study. A blinded team will review the safety data on a monthly basis.

4.2. INTERIM ANALYSIS

One interim analysis will be performed once all subjects randomized have completed their 12 week assessments. The aim of this analysis is to obtain preliminary results on the primary and secondary efficacy endpoints to be used for strategic and business purposes only. An unblinded team will run the analysis on the primary and secondary efficacy endpoints and the results will be shared with a limited number of people that will be described in a dedicated charter.

4.3. FINAL ANALYSIS

All final, planned analyses identified in this SAP will be performed by IQVIA Biostatistics following Sponsor Authorization of this Statistical Analysis Plan, Database Lock, Sponsor Authorization of Analysis Sets and Unblinding of Treatment.

5. ANALYSIS SETS

Agreement and authorization of subjects included/excluded from each analysis set will be conducted prior to the unblinding of the study.

5.1. ALL ENROLLED ANALYSIS SET [ENR]

The all enrolled (ENR) set will contain all subjects who signed informed consent for this study.

5.2. ALL RANDOMISED ANALYSIS SET [RND]

The all randomised (RND) set will contain all subjects in the ENR set who were randomised to study medication.

For analyses and displays based on RND, subjects will be classified according to randomised

Document:	x:\biostatistics\documentation\sap\pya18238_izana_ izn-101	_sap_v1_0_2019050.docx	
Author:		Version Number:	1.0
		Version Date:	07May2019
Template No.:	CS_TP_BS016 Revision 5	Reference: CS_WI	_BS00

Effective Date: 01Apr2018

Izana Bioscience Limited PROTOCOL IZN-101

Statistical Analysis Plan

treatment.

5.3. FULL ANALYSIS SET [FAS]

The full analysis set (FAS) will contain all subjects in the RND set who received at least one dose of study medication.

The intent-to-treat principle is preserved, despite the exclusion of subjects randomised who did not take the study medication, because the decision of whether or not to begin the treatment could not be influenced by knowledge of the assigned treatment, i.e. the study medication is blinded.

For analyses and displays based on FAS, subjects will be classified according to randomised treatment.

5.4. COMPLETERS ANALYSIS SET (S) [COM]

The completers analysis set (COM) will contain all subjects in the FAS that have week 12 efficacy data and subjects will be classified according to the randomised treatment.

5.5. PER PROTOCOL ANALYSIS SET [PPAS]

The per-protocol analysis set (PPAS) will contain all subjects in the COM who did not experience any protocol deviations that might affect the efficacy results. Protocol deviations for exclusion will be defined and detailed in a separate document to be agreed and signed by IQVIA and the Sponsor before database lock.

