14.2. SECONDARY EFFICACY

The secondary efficacy analyses will be performed for FAS and PPAS.

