14.2.1. SECONDARY EFFICACY VARIABLES & DERIVATIONS

14.2.1.1. Proportion of subjects who achieve an ASAS40 clinical response at Week 12

ASAS40 responder is defined as follow:

A subject with an improvement from baseline of at least 40% and an absolute improvement of at least 20 units on a 0-100 VAS scale in at least 3 of the following four domains derived on the eCRF and no worsening at all in the fourth domain:

- o Subject's Global Assessment of Disease Status,
- Subject's Assessment of Spinal Pain,
- Function (overall BASFI score),
- Inflammation, (average of the last 2 questions of BASDAI: intensity of morning stiffness, duration of morning stiffness)

The data used to calculate ASAS40 are collected in the eCRF at Baseline and Visit 6 (week 12).

14.2.1.2. Proportion of subjects who achieve an ASAS20 clinical response at Week 6

ASAS20 responder is defined as described in the primary efficacy endpoint Section 14.1.1

14.2.1.3. Proportion of subjects who achieve ASDAS-CRP response at Weeks 6 and 12

ASDAS-CRP scores is derived in the eCRF (according to the formula defined in Section 8.1 of

Document:	x:\biostatistics\documentation\sap\pya18238_izana_izn-101	_sap_v1_0_2019050.docx	
Author:		Version Number:	1.0
		Version Date:	07May2019
Template No.	CS_TP_BS016 Revision 5	Reference: CS_W	_BS00

Effective Date: 01Apr2018

the protocol).

The disease activity states are defined as follows:

ASDAS-CRP score	Activity states
<1.3	Inactive disease
\geq 1.3 and <2.1	Moderate disease activity
\geq 2.1 and \leq 3.5	High disease activity
>3.5	Very high disease activity

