14.2.2. MISSING DATA METHODS FOR SECONDARY EFFICACY VARIABLE(S)

Subjects with missing primary endpoint data (either at Baseline or Week 12) will be treated as non-responders.

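### The Week 6 per-protocol results depend on what happens to subjects after Week 6 (minor; supportive analysis only)

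*SAP*

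**What the plan says.** SAP 5.4 restricts the completers set to "all subjects in the FAS that have week 12 efficacy data". SAP 5.5 builds the PPAS on it: the PPAS "will contain all subjects in the COM who did not experience any protocol deviations that might affect the efficacy results". It sets no time limit on those deviations and leaves the list for later: "Protocol deviations for exclusion will be defined and detailed in a separate document".

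On use of the sets, SAP 14.2 states: "The secondary efficacy analyses will be performed for FAS and PPAS". Two of the secondary endpoints in SAP 14.2.1 are read at Week 6: "Proportion of subjects who achieve an ASAS20 clinical response at Week 6" and "Proportion of subjects who achieve ASDAS-CRP response at Weeks 6 and 12". SAP 14.2.3.1 tests the secondary endpoints with Fisher's exact test. No Week 6 version of the PPAS is defined.

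Protocol 9.3 makes the FAS the primary efficacy set and the per-protocol set secondary. SAP 3.3 records that the per-protocol definition was changed for two reasons. The protocol's Week 10 data requirement was a typing error for Week 12, and the set should also show the effect in patients who kept to the protocol. It does not discuss the Week 6 endpoints.

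**The concern.** A per-protocol result at Week 6 should describe subjects who were treated and assessed as planned up to Week 6. Under SAP 5.4 and 5.5, membership also depends on the following six weeks: whether Week 12 data exist and, as far as the SAP goes, whether a deviation occurred at any time.

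Those later events may be related to how the subject was doing at Week 6. Protocol Appendix 5 counts use of an excluded medication as a violation, and its list includes most NSAID dose changes before the end of Week 12. A subject still in pain at Week 6 is a plausible candidate for such a change, or for withdrawal. The set may then select on a consequence of the outcome it is estimating. If the FAS and PPAS disagreed at Week 6, a reader could not tell whether the cause was protocol adherence up to Week 6 or selection afterwards. The placebo arm has only 6 subjects, so a single exclusion is visible.

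**Working it through.** The plan states no figure on this point, so there is none to reproduce. The check traces the set definitions and then illustrates the size.

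**1. Set membership**

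- PPAS lies within COM, and COM within FAS (SAP 5.3 to 5.5).
- COM requires Week 12 efficacy data (SAP 5.4).
- The Week 6 endpoints are run on the PPAS (SAP 14.2, 14.2.1).
- So a subject with valid Week 6 data and no Week 12 data is outside the Week 6 PPAS analysis.

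**2. Who is clearly affected**

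- SAP 6.3 maps early-termination data to the next available visit for by-visit summaries. For a subject who stops between Weeks 6 and 10, that visit is Week 10, so the Week 12 condition still fails.
- A subject who stops after Week 10 and attends the early-termination visit may have data mapped to Week 12 and stay in COM.
- A subject with neither a Week 12 nor an early-termination assessment is out.
- A subject with a deviation after Week 6 is out unless the separate document limits deviations by visit.

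**3. Illustration in counts**

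Arm sizes of 36 and 6 are from SAP 3.1. The Week 6 responder counts are assumed, close to the planning rates of 0.6 and 0.3 (Protocol 1.1), which apply to Week 12. Fisher p-values are two-sided.

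| Lost after Week 6 | Namilumab | Placebo | Difference (points) | Fisher p |
|---|---|---|---|---|
| none | 22/36 = 61.1% | 2/6 = 33.3% | 27.8 | 0.375 |
| 4 namilumab non-responders | 22/32 = 68.8% | 2/6 = 33.3% | 35.4 | 0.167 |
| 6 namilumab non-responders | 22/30 = 73.3% | 2/6 = 33.3% | 40.0 | 0.15 |
| 1 placebo non-responder | 22/36 = 61.1% | 2/5 = 40.0% | 21.1 | 0.633 |
| 2 placebo non-responders | 22/36 = 61.1% | 2/4 = 50.0% | 11.1 | 1.0 |
| 1 placebo responder | 22/36 = 61.1% | 1/5 = 20.0% | 41.1 | 0.15 |

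With a set defined at Week 6, the first row would stand whatever happened later.

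**4. Illustration in expectation**

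Let p be the true Week 6 response rate, and let qR and qN be the proportions of Week 6 responders and non-responders lost afterwards. The rate shown in the PPAS is

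p(1 − qR) / [p(1 − qR) + (1 − p)(1 − qN)].

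The documents give no loss rates, so every q below is an assumption.

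- **Equal loss by arm, more among non-responders** (qR 0.02, qN 0.20; true 50% vs 25%): 0.49/(0.49 + 0.40) = 0.551 and 0.245/(0.245 + 0.60) = 0.290. Both rates rise; the difference is 26 points against a true 25.
- **Same pattern at the planning rates** (qR 0.05, qN 0.20; true 60% vs 30%): 0.57/(0.57 + 0.32) = 0.640 and 0.285/(0.285 + 0.56) = 0.337. The difference goes from 0.300 to 0.303.
- **Equal loss by arm, more among responders** (qR 0.20, qN 0.02; true 50% vs 25%): 0.40/(0.40 + 0.49) = 0.449 and 0.20/(0.20 + 0.735) = 0.214. Both rates fall.
- **More loss among placebo non-responders** (qR 0.02; qN 0.15 namilumab, 0.40 placebo; true 50% vs 25%): 0.49/(0.49 + 0.425) = 0.536 and 0.245/(0.245 + 0.45) = 0.353. The difference falls from 25 to 18 points.
- **The reverse** (qR 0.02; qN 0.40 namilumab, 0.15 placebo): 0.49/(0.49 + 0.30) = 0.620 and 0.245/(0.245 + 0.6375) = 0.278. The difference rises to 34 points.
- **No true difference, both 40%** (qR 0.02; qN 0.10 namilumab, 0.40 placebo): 0.392/(0.392 + 0.54) = 0.421 and 0.392/(0.392 + 0.36) = 0.521. A spurious 10 points appears in favour of placebo.

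**The case against.** A reader might infer that Week 6 non-responders vanish from the analysis, so that both arms' rates are inflated, or that the rule flatters namilumab. The documents do not support either reading. The rule also removes Week 6 responders who leave or deviate later. Inflation needs heavier loss among non-responders, and the effect on the difference can go either way.

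Four further objections carry weight.

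- **Reach.** Only a supportive version of two secondary endpoints is affected. The FAS ranks first, retains these subjects and is also run for every secondary endpoint. In none of the count examples does the Fisher p-value come near 0.05.
- **Size.** Material bias in the difference needs clearly unequal loss. With 40% of placebo non-responders lost, 6 × (0.75 × 0.40 + 0.25 × 0.02) = 1.8 of 6 placebo subjects leave the set after Week 6 (about 30%), against 0.5 × 0.15 + 0.5 × 0.02 = 8.5% on namilumab. The plan expects all 42 randomised subjects to be evaluable.
- **Unknown document.** The separate deviation list may limit deviations by visit, and SAP 5 requires set membership to be agreed before unblinding. It is therefore not established that a deviation after Week 6 removes a subject, only that the SAP sets no limit. That list would not lift the Week 12 data requirement, which stands in the SAP itself.
- **Nature of the set.** Any per-protocol set conditions on events after randomisation. A Week 6 set would still select on dropout and deviation up to Week 6. This stands, but it does not justify adding selection on events after the assessment being analysed.

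**Conclusion.** The point holds as a minor one. On the text of SAP 5.4, 5.5 and 14.2, the Week 6 per-protocol results are conditioned on later events. This is clear for subjects who stop between Weeks 6 and 10 or who have no Week 12 or early-termination assessment. For later deviations it holds unless the separate document limits them by visit.

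The direction of bias cannot be stated in advance. If non-responders are lost more often than responders, both rates rise. Similar loss in both arms leaves the difference almost unchanged, and unequal loss can move it materially. In the assumed data, losing one placebo non-responder raises the placebo rate by about 7 points. The rates and loss proportions behind these figures are illustrations, not estimates from the documents.

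This selection rule leaves the FAS results and the Week 12 endpoints untouched.

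**What to change.** In SAP 5.5, add that for a secondary endpoint at visit v the PPAS consists of FAS subjects with efficacy data at visit v and no efficacy-affecting deviation on or before visit v. Keep the present definition for the Week 12 endpoints. The separate deviation document should record the date or visit of each excluding deviation so that the rule can be applied.

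One linked sentence needs attention. SAP 14.2.2 reads: "Subjects with missing primary endpoint data (either at Baseline or Week 12) will be treated as non-responders". Taken literally, it would score a Week 6 responder without Week 12 data as a non-responder at Week 6, even once that subject is back in the set. SAP 14.3.2 describes the rule as applying to missing data at the timepoint of interest, and SAP 14.2.2 should say the same. This is a scoring rule, separate from the selection rule, and correcting one does not correct the other.

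The cost is one sentence in SAP 5.5 and one inclusion flag per visit. The downside is that the PPAS will differ in size between Week 6 and Week 12, so tables should show the denominator at each visit.

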5.6. SAFETY ANALYSIS SET [SAF]

The safety analysis set (SAF) will contain all subjects in the RND set who receive at least one dose of study medication and subjects will be classified according to treatment received. If there is any doubt whether a subject was treated or not, they will be assumed as treated for the purposes of analysis and classified according to the randomised treatment.

 Document:
 x:\biostatistics\documentation\sap\pya18238_izana_izn-101_sap_v1_0_2019050.docx

 Author:
 Version Number:
 1.0

 Version Date:
 07May2019

 Template No.:
 CS_TP_BS016 Revision 5
 Reference:
 CS_WI_BS00

Effective Date: 01Apr2018

6. GENERAL CONSIDERATIONS

6.1. REFERENCE START DATE AND STUDY DAY

Study Day will be calculated from the reference start date and will be used to show the start/ stop day of assessments and events and will appear in every listing where an assessment date or event date appears.

Reference start date is defined as the day of the first dose of study medication, (Day 1 is the day of the first dose of study medication).

• If the date of the assessment or event is on or after the reference date:

Study Day = (date of event - reference date) + 1.

• If the date of the assessment or event is prior to the reference date:

Study Day = (date of event – reference date).

In the situation where the assessment or event date is partial or missing, the date will appear as partial or missing in the listings, and Study Day, and any corresponding durations will be presented based on the imputations specified in 17, if defined, otherwise they will appear as missing.

6.2. BASELINE

Unless otherwise specified, baseline is defined as the last non-missing measurement taken prior to the reference start date (including unscheduled assessments). In the case where the last non-missing measurement and the reference start date coincide, that measurement will be considered pre-baseline, but Adverse Events (AEs) and medications commencing on the reference start date will be considered post-baseline.

6.3. RETESTS, UNSCHEDULED VISITS AND EARLY TERMINATION DATA

In general, for by-visit summaries, data recorded at the nominal visit will be presented. Unscheduled measurements will not be included in by visit summaries but will contribute to the

Document:	x:\biostatistics\documentation\sap\pya18238_izana_ izn-101	_sap_v1_0_2019050.docx	
Author:		Version Number:	1.0
		Version Date:	07May2019
Template No.:	CS_TP_BS016 Revision 5	Reference: CS_WI	_BS00

Effective Date: 01Apr2018

best/ worst case value where required (e.g. shift table).

In the case of a retest (same visit number assigned), the earliest available measurement for that visit will be used for by-visit summaries.

Early termination data will be mapped to the next available visit number for by-visit summaries. Listings will include scheduled, unscheduled, retest and early discontinuation data.

6.4. WINDOWING CONVENTIONS

No visit windowing will be performed for this study.

6.5. STATISTICAL TESTS

The default significance level will be 5%; confidence intervals will be 95% and all tests will be two-sided, unless otherwise specified in the description of the analyses.

6.6. COMMON CALCULATIONS

For quantitative measurements, change from baseline will be calculated as:

• Test Value at Visit X – Baseline Value

6.7. SOFTWARE VERSION

All analyses, summaries and listings will be performed using SAS[®] software (version 9.4 or higher).

7. STATISTICAL CONSIDERATIONS

7.1. DESCRIPTIVE STATISTICS

If not otherwise specified, categorical variables will be summarized by counts and percentages and continuous variables by mean, standard deviation (SD), median, min and max.

Document:	x:\biostatistics\documentation\sap\pya18238_izana_ izn-101	_sap_v1_0_2019050.docx	
Author:		Version Number:	1.0
		Version Date:	07May2019
Template No.:	CS_TP_BS016 Revision 5	Reference: CS_W	_BS00

Effective Date: 01Apr2018

7.2. ADJUSTMENTS FOR COVARIATES AND FACTORS TO BE INCLUDED IN ANALYSES

No adjustment for covariates will be used in the primary analysis.

7.3. MULTICENTRE STUDIES

This study will be conducted by multiple investigators at multiple centres in UK. Randomisation to treatment arms is not stratified by centre.

